## 9.5 Analysis Populations

The following populations are defined for the analysis and reporting of data. All participants will be reported, and their data analyzed, according to the treatment(s) they actually received.

*All Participants as Treated (APasT)*: The All Participants as Treated Population consists of all participants who received at least one dose of treatment. This population will be used for assessments of safety and tolerability.

*Per-Protocol (PP)*: The Per-Protocol Population consists of the set of data generated by the subset of participants who comply with the protocol sufficiently to ensure that these data will be likely to exhibit the effects of treatment, according to the underlying scientific model. Compliance covers such considerations as exposure to treatment, availability of

measurements and absence of important protocol deviations. Important protocol deviations will be identified to the extent possible prior to unblinding by individuals responsible for data collection/compliance, and its analysis and interpretation. Any participants or data values excluded from analysis will be identified, along with their reason for exclusion, in the CSR. At the end of the study, all participants who are compliant with the study procedure as aforementioned and have available data from at least one treatment (dose level) will be included in the Per-Protocol dataset. This population will be used for the PK analysis.

#### 9.6 Statistical Methods

#### Safety:

For primary objective, all AEs and AEs leading to discontinuation of study intervention will be summarized and tabulated.

Summary statistics and plots will be generated for raw laboratory safety tests, 12-lead ECGs, and/or VS as well as for change from baseline, as deemed clinically appropriate. Depending on the safety parameter, the difference from baseline will either be computed on the original scale (raw change from baseline) or on the log scale and back transformed for reporting (percent change from baseline).

For exploratory purposes, summary statistics and plots will be generated for BARS, AIMS, SAS, as well as for change from baseline. Responses to the C-SSRS will be listed. Additionally, summary statistics for change in MMSE-2 and NPI from baseline will be provided.

#### Pharmacokinetics:

Individual C24hr values will be listed, and the following (non-model-based) descriptive statistics will be provided: N (number of subjects with non-missing data), arithmetic mean, standard deviation, arithmetic percent CV (calculated as 100 x standard deviation/arithmetic mean), median, minimum, maximum, geometric mean, and geometric percent CV (calculated as 100 x sqrt(exp( $s^2$ ) - 1), where  $s^2$  is the observed variance on the natural log-scale).

The exploratory objective pertaining to the assessment of relationship between CYP2C9 genetic polymorphs and the laboratory and PK of MK-8189, and the relationship between genetic variation and response to the treatment may be addressed in a separate report.

#### 9.7 Interim Analyses

During the in-life portion of the trial, descriptive summary level results (safety labs, VS, ECGs) will be prepared as needed to support decision-making meetings. No individual participant level results will be provided. There are no planned interim analyses to test any formal hypotheses.

MK-8189-017-04 FINAL PROTOCOL

21-IIII-2022

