#### 4 STUDY DESIGN

#### 4.1 Overall Design

This is a randomized, placebo-controlled, parallel-group, multisite, double-blind study of MK-8189 in participants with Alzheimer's Disease with and without neuropsychiatric symptoms. To most closely simulate the patient population for the indication evaluated, it is preferred that participants included in this study have symptoms of agitation-aggression or psychosis (defined as a severity of score  $\geq 1$  and frequency score of  $\geq 2$  on the NPI Agitation-Aggression and/or Delusions and/or Hallucinations domains).

Up to approximately 28 participants will be enrolled to ensure at least 16 participants complete the study. Note: Greater than 16 participants may be required to complete the study if additional study data are needed to further understand the safety and tolerability profile of MK-8189 in the AD population.

This is an outpatient study as participants will be dosing at home and will require visits to the CRU per the SoA. Therefore, participants must have a trial partner/caregiver as described in the inclusion/exclusion criteria.

The first 8 participants will be randomized to receive MK-8189 8 mg/placebo QD Days 1-3, 16 mg/placebo QD Days 4-28 (Titration 1). Participants may be down-titrated by the investigator at any time without consultation of the Sponsor in the case of safety or tolerability issues. Changes in the dosage regimen will be communicated to the Sponsor and the Sponsor will document changes in a Protocol Clarification Letter. After approximately 8 participants have completed approximately 3 weeks of dosing, AE data will be reviewed to determine whether to continue to enroll participants at the Titration 1 regimen or whether participants should receive an alternate dosing regimen (e.g., MK-8189 8 mg/placebo QD Days 1-3, 16 mg/placebo QD Days 4-6, 24 mg/placebo Days 7-28 (Titration 2) OR MK-8189 4 mg /placebo QD Days 1-3, 8 mg/placebo Days 4-6, 16 mg Days 7-9, 24 mg Days 10-28 (Titration 3)). Prior to initiation of an alternate regimen that includes escalation to a dose above 16 mg, the PK data from the initial cohort of participants will be required to be reviewed. The decision will be made jointly between the investigators and the Sponsor and any change to the dosing regimen will be documented in a Protocol Clarification Letter. See section 6.6 for allowed dose modifications.

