### 4.3 Justification for Dose

Currently the efficacious dose of MK-8189 is unknown, however, based on data from in vivo preclinical assays (see Section 2.1 and the IB), enzyme occupancy of 30% is expected to be required for efficacy in neuropsychiatric symptoms associated with dementia. A dose of 8 mg is expected to result in a mean C24 (90% confidence interval) enzyme occupancy of approximately 40% (34, 47). Proof of concept has been established for 12 mg of MK-8189 in schizophrenia patients (P005), however, doses up to and including 24 mg are being evaluated in a Phase 2b study (P008) to understand if greater efficacy is observed with higher doses. Recent literature suggests that for antipsychotics to be effective in the treatment of behavioral symptoms associated with dementia, doses may need to be similar to those used for the treatment of schizophrenia [Grossberg, G. T., et al 2020]. Preliminary PK data from P011 suggest the median C24 value in healthy elderly following multiple doses of MK-8189 16 mg will be similar to that observed following multiple 24 mg doses of MK-8189 in non-elderly adults with schizophrenia. Therefore, the initial titration regimen in the current study will escalate MK-8189 doses up to 16 mg. If multiple doses of MK-8189 16 mg is generally well tolerated in the initial cohort of ~8 participants and, based on a PK analysis of these participants, MK-8189 exposure is less than anticipated and thus closer to exposures observed in younger (< 60 years of age) adult participants, an alternate titration regimen escalating to 24 mg of MK-8189 (Titration Regimen 2) may be explored.

As this is a Phase 1 assessment of MK-8189 in humans, and the PK, pharmacodynamic and safety profiles of the compound are still being evaluated, modifications to the dose or dosing regimen may be required to achieve the scientific goals of the study objectives and/or to ensure appropriate safety monitoring of the study participants. Details of allowed modifications are provided in Section 8.10.7.

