## 6.3.3 Blinding

A double-blinding technique with in-house blinding will be used. MK-8189 will be packaged identically to the matching placebo so that blind is maintained. The participant, the trial partner/caregiver, the investigator, and Sponsor personnel or delegate(s) who are involved in

the study intervention administration or clinical evaluation of the participants are unaware of the intervention assignments.

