#### 6.6 **Dose Modification (Escalation/Titration/Other)**

The dose regimen for this trial is MK-8189 8mg/placebo Days 1-3 days followed by 16 mg/placebo Days 4-28 (Titration 1).

Following MK-8189/placebo treatment of approximately 8 participants for approximately 3 weeks, a decision will be made to continue dosing newly enrolled participants with the current regimen or modify to an alternate regimen. The following alternate treatment regimens may be explored during the study following a review of safety and tolerability data and a discussion with the investigators and the Sponsor. However, dose escalation above 16 mg will not occur without a review of PK data from the initial cohort of approximately 8 participants. Any change in the treatment regimen will be documented in a Protocol Clarification Letter.

- 8 mg/matched placebo Days 1-3, 16 mg/placebo Days 4-6 and 24 mg/placebo Days 7-28 (Titration 2)
- 4 mg/matched placebo Days 1-3, 8 mg/placebo Days 4-6, 16 mg/placebo Days 7-9 and 24 mg/placebo Days 10-28 (Titration 3)
- Other more conservative regimen

If medical care necessitates participants may:

- Skip a single dose and dosing may continue at the same dose level or adjusted downwards.
- Receive the same dose level to further explore safety and tolerability at that level.
- Receive a lower dose of the study intervention.
- Stop dosing.

Any change in dosing regimen will be documented in a Protocol Clarification Letter.

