## 8.1.10 Participant Blinding/Unblinding

STUDY INTERVENTION IDENTIFICATION INFORMATION IS TO BE UNMASKED ONLY IF NECESSARY FOR THE WELFARE OF THE PARTICIPANT. EVERY EFFORT SHOULD BE MADE NOT TO UNBLIND.

For emergency situations where the investigator or medically qualified designee (consistent with local requirements) needs to identify the intervention used by a participant and/or the dosage administered, he/she will contact the emergency unblinding call center by telephone

and make a request for emergency unblinding. As requested by the investigator or medically qualified designee, the emergency unblinding call center will provide the information to him/her promptly and report unblinding to the Sponsor. Before contacting the emergency unblinding call center to request unblinding of a participant's intervention assignment, the investigator who is qualified physician should make reasonable attempts to enter the intensity of the AEs observed, the relation to study intervention, the reason thereof, etc, in the medical record. If it is not possible to record this assessment in the medical record before the unblinding, the unblinding should not be delayed.

If unblinding has occurred, the circumstances around the unblinding (eg, date, reason, and person performing the unblinding) must be documented promptly, and the Sponsor Clinical Director notified as soon as possible.

Once an emergency unblinding has taken place, the investigator, site personnel, and Sponsor personnel may be unblinded so that the appropriate follow-up medical care can be provided to the participant.

Participants whose treatment assignment has been unblinded by the investigator or medically qualified designee and/or nonstudy treating physician must be discontinued from study intervention, but should continue to be monitored in the study.

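### Does it matter that the in-life summaries listed in Section 9.7 omit the AE and PK data behind the regimen decision?

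*Combined protocol and SAP*

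**What the plan says.** Section 9.7 states that "descriptive summary level results (safety labs, VS, ECGs) will be prepared as needed to support decision-making meetings". It adds that results for single participants will not be provided and that no formal hypothesis is tested at an interim look.

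The decision these outputs would support is described elsewhere:

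- Section 4.1: after about 8 participants have had about 3 weeks of dosing, "AE data will be reviewed to determine whether to continue to enroll participants at the Titration 1 regimen" or move to another one. Before a regimen above 16 mg, "the PK data from the initial cohort of participants will be required to be reviewed". On who decides: "The decision will be made jointly between the investigators and the Sponsor".
- Section 6.6 repeats the PK condition: "dose escalation above 16 mg will not occur without a review of PK data from the initial cohort of approximately 8 participants". It describes the safety input more broadly than 4.1, as data on safety and tolerability.
- Section 4.3 makes the 24 mg option depend on tolerability and on whether, "based on a PK analysis of these participants, MK-8189 exposure is less than anticipated and thus closer to exposures observed in younger" adults.

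On blinding, Section 6.3.3 says "A double-blinding technique with in-house blinding will be used". It then lists those kept unaware: the participant, the trial partner, the investigator, and Sponsor staff who take part in administration or clinical evaluation. Section 8.1.10 opens with "STUDY INTERVENTION IDENTIFICATION INFORMATION IS TO BE UNMASKED ONLY IF NECESSARY FOR THE WELFARE OF THE PARTICIPANT". Section 6.8 restricts the unblinding call center to emergencies.

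**The concern.** Read side by side, the statistical section and the design do not match. The only text in Section 9 on in-life outputs names laboratory tests, vital signs and ECGs. The design section names AEs, which are the primary endpoint, and PK. A decision package built strictly from the 9.7 list would contain neither.

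The PK step raises a second question. A summary of MK-8189 exposure requires separating recipients from placebo participants, either with the codes or from the measured concentrations, which themselves show who took the drug. Section 8.1.10 allows unmasking only for participant welfare, and no exception is written for this review. Taken literally, that rule sits badly with the PK review that Section 6.6 requires before going above 16 mg.

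At stake would be the traceability of the trial's main adaptive decision and the documentation of the blind, while AEs in some of the same participants are still being collected.

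**Working it through.** The plan states no figure to reproduce. The check is mainly a comparison of sections, with some arithmetic for context.

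**1. Inputs against outputs.** Inputs in 4.1: {AE, PK}. Outputs in 9.7: {labs, vital signs, ECGs}. Overlap: 0 of 2. The count depends on which section defines the input. Section 6.6 bases the same decision on safety and tolerability data. Section 4.2.1.2 says safety and tolerability are assessed through AEs together with examinations, ECGs, vital signs and laboratory tests. On that wording, all three outputs in 9.7 serve the decision. What 9.7 leaves out is a mention of AEs and PK, and its list does not claim to be complete.

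**2. Does the AE review need a 9.7 output?** No. Section 4.1 prescribes the review directly. Site staff review and record AEs in daily calls (Section 8.10.4), and AEs reach the Sponsor through electronic data collection (Section 10.3.5). The people who decide, the investigators and the Sponsor, already hold the data.

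**3. Does the PK review break the blinding rules?** Section 6.3.3 limits the blinded Sponsor staff to those in administration or clinical evaluation, and the blinding roles in the synopsis (Section 1.1) do not include the Sponsor. After its opening rule, Section 8.1.10 deals with emergencies: the call to the center, recording the event beforehand, and discontinuing the unblinded participant. Section 6.8 concerns the same call center. Neither section addresses an analyst outside the 6.3.3 list. A PK analyst with code access is therefore compatible with the plan.

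**4. Is the preparer unknown?** Only in part. Section 9.2 names Early Clinical Development Statistics with two pharmacology departments, one of them Quantitative Pharmacology and Pharmacometrics. Section 8.6 gives the Sponsor the choice of samples to assay. Sections 4.4 and 8.10.7 foresee a pause for PK review. What is missing is the assignment of this particular task and those staff members' blinding status.

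**5. Context figures.**

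- Follow-up remaining: the AE window is 28 dosing days + 14 follow-up days = 42 days. At day 21, 42 − 21 = 21 days remain, or 21/42 = 50%. This holds only for a participant exactly at week 3. With staggered enrolment, earlier participants have less left.
- Recipients in the first 8: 8 × 21/28 = 6 expected on MK-8189 and 2 on placebo. Complete blocks of 4 at 3:1 would give exactly 6. No block size is given. If the first 8 are treated as a simple random draw from 21 active and 7 placebo, P(a active) = C(21,a) × C(7,8−a) / C(28,8). This gives 22.9% for 5, 36.7% for 6 and 26.2% for 7, which sum to 85.8%. The calculation ignores the two strata filling from opposite ends of the schedule.

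These figures show that the split in the first cohort is not fixed by the text, so someone must identify the recipients before exposure can be summarised. They do not show bias in any estimate.

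**The case for a change.** The strongest case for a change is that this is the trial's one adaptive decision, that it rests on the primary endpoint and on a PK gate, and that a few sentences would document it: AE and C24hr summaries added to 9.7, a named department with code access, and a line in 6.3.3 recording that access. The decision is shared with blinded investigators. The plan does not say whether they see AEs pooled or by arm, or how PK reaches them. Section 9.7 bars participant-level results but is silent on summaries by arm.

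Most of the factual part stands. 9.7 names neither input, and no section assigns the in-life PK review, states those staff members' blinding status or describes what blinded decision makers are shown. What does not stand is the stronger reading, that Sections 6.6 and 8.1.10 cannot both be followed or that nobody is responsible for the analysis.

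More detailed text would also need care. With about 2 placebo participants expected, AE summaries by arm would come close to showing individual results. C24hr split by actual dose in about 6 recipients, with down-titration allowed, could leave cells of 1 or 2, in effect the participant-level results that 9.7 withholds.

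**Conclusion.** No change to the plan is called for. The omission is real but is missing detail of a kind that the Sponsor's staff can fill sensibly: the AE review is already required by Section 4.1, and a PK analyst outside the blinded roles can prepare a summary-level exposure result for the joint meeting.

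The effect on results is nil. C24hr is summarised descriptively, the final AE tables use all treated participants, and there is no hypothesis, power calculation or error rate to disturb. The PK step does not arise if the trial stays at or below 16 mg. What remains is traceability: where a regimen above 16 mg is considered, the trial file should show who saw the codes and what the investigators were given. That is good practice in running the review and does not depend on amending Section 9.7.

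The conclusion assumes that the list in 9.7 is illustrative, as its wording allows, and that the blinded roles are those listed in Section 6.3.3 and the synopsis. If in-house blinding were meant to cover every Sponsor function, including PK analysis, the arrangement would need to be written down. The documents do not define the term that way.

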## 9.8 Multiplicity

Since there are no pre-specified hypotheses, no adjustments for multiplicity are needed.

#### 9.9 Sample Size and Power Calculations

Since there are no hypotheses, no power calculations are provided

#### 10 SUPPORTING DOCUMENTATION AND OPERATIONAL CONSIDERATIONS

#### 10.1 Appendix 1: Regulatory, Ethical, and Study Oversight Considerations

#### **10.1.1** Code of Conduct for Clinical Trials

#### Merck Sharp & Dohme LLC, Rahway, NJ, USA (MSD)

#### **Code of Conduct for Interventional Clinical Trials**

#### I. Introduction

#### A. Purpose

MSD, through its subsidiaries, conducts clinical trials worldwide to evaluate the safety and effectiveness of our products. As such, we are committed to designing, implementing, conducting, analyzing, and reporting these trials in compliance with the highest ethical and scientific standards. Protection of participants in clinical trials is the overriding concern in the design and conduct of clinical trials. In all cases, MSD clinical trials will be conducted in compliance with local and/or national regulations (including all applicable data protection laws and regulations), and International Council for Harmonisation Good Clinical Practice (ICH-GCP), and also in accordance with the ethical principles that have their origin in the Declaration of Helsinki.

#### B. Scope

Highest ethical and scientific standards shall be endorsed for all clinical interventional investigations sponsored by MSD irrespective of the party (parties) employed for their execution (e.g., contract research organizations, collaborative research efforts). This Code is not intended to apply to trials that are observational in nature, or which are retrospective. Further, this Code does not apply to investigator-initiated trials, which are not under the full control of MSD.

#### II. Scientific Issues

#### A. Trial Conduct

#### 1. Trial Design

Except for pilot or estimation trials, clinical trial protocols will be hypothesis-driven to assess safety, efficacy and/or pharmacokinetic or pharmacodynamic indices of MSD or comparator products. Alternatively, MSD may conduct outcomes research trials, trials to assess or validate various endpoint measures, or trials to determine patient preferences, etc.

The design (i.e., participant population, duration, statistical power) must be adequate to address the specific purpose of the trial and shall respect the data protection rights of all participants, trial site staff and, where applicable, third parties. All trial protocols are and will be assessed for the need and capability to enroll underrepresented groups. Participants must meet protocol entry criteria to be enrolled in the trial.

#### 2. Site Selection

MSD's clinical trials are conducted globally in many different countries and in diverse populations, including people of varying age, race, ethnicity, gender, and accounting for other potential disease related factors. MSD selects investigative sites based on medical expertise, access to appropriate participants, adequacy of facilities and staff, previous performance in clinical trials, as well as budgetary considerations. Prior to trial initiation, sites are evaluated by MSD personnel (or individuals acting on behalf of MSD) to assess the ability to successfully conduct the trial.

Where appropriate, and in accordance with regulatory authority guidance, MSD will make concerted efforts to raise awareness of clinical trial opportunities in various communities. MSD will seek to engage underrepresented groups and those disproportionately impacted by the disease under study. MSD will support clinical trial investigators to enroll underrepresented groups and expand access to those who will ultimately use the products under investigation.

#### 3. Site Monitoring/Scientific Integrity

Investigative trial sites are monitored to assess compliance with the trial protocol and Good Clinical Practice (GCP). MSD reviews clinical data for accuracy, completeness, and consistency. Data are verified versus source documentation according to standard operating procedures. Per MSD policies and procedures, if potential fraud, scientific/research misconduct, privacy incidents/breaches or Clinical Trial-related Significant Quality Issues are reported, such matters are investigated. When necessary, appropriate corrective and/or preventative actions are defined and regulatory authorities and/or ethics review committees are notified.

